16.8 MISSING DATE INFORMATION FOR PRIOR OR CONCOMITANT MEDICATIONS

For prior or concomitant medications, including rescue medications, incomplete (i.e., partly missing) start dates and/or stop dates will be imputed. When the start date and the stop date are both incomplete for a subject, the start date will be imputed first.

16.8.1 Incomplete Start Date

The following rules will be applied to impute the missing numeric fields for an incomplete prior or concomitant medication start date. If the stop date is complete (or imputed) and the imputed start date is after the stop date, the start date will be imputed using the stop date.

Missing month and day

- If the year of the incomplete start date is the same as the year of the first dose of double-blind investigational product, the month and day of the first dose of double-blind investigational product will be assigned to the missing fields
- If the year of the incomplete start date is before the year of the first dose of double-blind investigational product, *December 31* will be assigned to the missing fields

Page 47 of 53

• If the year of the incomplete start date is after the year of the first dose of double-blind investigational product, *January 1* will be assigned to the missing fields

Missing month only

• If only the month is missing, the day will be treated as missing and both the month and the day will be replaced according to the above procedure

Missing day only

- If the month and year of the incomplete start date are the same as the month and year of the first dose of double-blind investigational product, the day of the first dose of double-blind investigational product will be assigned to the missing day
- If either the year of the incomplete start date is before the year of the date of the first dose of double-blind investigational product or if both years are the same but the month of the incomplete start date is before the month of the date of the first dose of double-blind investigational product, the last day of the month will be assigned to the missing day
- If either the year of the incomplete start date is after the year of the date of the first dose of double-blind investigational product or if both years are the same but the month of the incomplete start date is after the month of the date of the first dose of double-blind investigational product, the first day of the month will be assigned to the missing day

16.8.2 Incomplete Stop Date

The following rules will be applied to impute the missing numeric fields for an incomplete prior or concomitant medication stop date. If the date of the last dose of double-blind investigational product is missing, impute it as described in Section 16.4. If the imputed stop date is before the start date (imputed or nonimputed start date), the imputed stop date will be equal to the start date.

Missing month and day

- If the year of the incomplete stop date is the same as the year of the last dose of double-blind investigational product, the month and day of the last dose of double-blind investigational product in the study will be assigned to the missing fields
- If the year of the incomplete stop date is before the year of the last dose of double-blind investigational product, *December 31* will be assigned to the missing fields

Page 48 of 53

• If the year of the incomplete stop date is after the year of the last dose of double-blind investigational product, *January 1* will be assigned to the missing fields

Missing month only

• If only the month is missing, the day will be treated as missing and both the month and the day will be replaced according to the above procedure

Missing day only

- If the month and year of the incomplete stop date are the same as the month and year of the last dose of double-blind investigational product, the day of the last dose of double-blind investigational product will be assigned to the missing day
- If either the year of the incomplete stop date is before the year of the date of the last dose of double-blind investigational product or if both years are the same but the month of the incomplete stop date is before the month of the date of the last dose of double-blind investigational product, the last day of the month will be assigned to the missing day
- If either the year of the incomplete stop date is after the year of the date of the last dose of double-blind investigational product or if both years are the same but the month of the incomplete stop date is after the month of the date of the last dose of double-blind investigational product, the first day of the month will be assigned to the missing day

16.9 CHARACTER VALUES OF CLINICAL LABORATORY PARAMETERS

If the reported value of a clinical laboratory parameter cannot be used in a statistical summary table because, for example, a character string is reported for a parameter of the numeric type, a coded value must be appropriately determined for use in the statistical analyses. The actual values, as reported in the database will be presented in the data listings.

Table 16.9–1 shows examples of how some possible laboratory results should be coded for analysis.

Page 49 of 53

Table 16.9–1. Examples of Coding Special Character Values for Clinical Laboratory Parameters

Laboratory Test, SI Unit	Possible Laboratory Results	Coded Value for Analysis
CHEMISTRY		 
ALT, U/L	< 5	5
AST, U/L	< 5	5
Bilirubin, total, μmol/L	< 2	2
URINALYSIS		
	< 2.775, Negative	0
	[2.775, 5.55)	1+
C1	[5.55, 13.875)	2+
Glucose, mmol/L	[13.875, 27.75)	3+
	[27.75, 55.5)	4+
	≥ 55.5	5+
141/T	$> 0.444, \ge 0.444, >0$, Trace	Positive
ketones, mmol/L	≤ 0, Negative	Negative
pH	> 8.0, ≥ 8.0	8.0
	≥ 8.5	8.5
	< 0, Negative	Negative
	[0, 0.15), Trace	0
Dustain a/I	[0.15, 0.3)	1+
Protein, g/L	[0.30, 1.0)	2+
	[1.0, 5.0)	3+
	>= 5.0	4+

ALT = alanine aminotransferase; AST = aspartate aminotransferase; SI = Le Système International d'Unités (International System of Units).

SAP SCT-MD-60 Allergan

Page 50 of 53

17.0 CHANGES TO ANALYSES SPECIFIED IN PROTOCOL

Only the following changes have been made to the protocol version 3.0: 30 Jun 2020.

Per protocol section 11.3, demographic parameters to be summarized include weight z-score and height z-score. However, these will be listed but not summarized.

No other changes have been made to the analyses specified in the protocol.

Page 51 of 53

19.0 APPENDICES

APPENDIX I PATTERN-MIXTURE MODEL DETAILS

For repeated measures with the monotone missing mechanism, the pattern-mixture model with non-future dependent missing assumption, proposed by Kenward et al. (2003), provides a feasible solution to accommodate certain missing not at random (MNAR) mechanism. The methodology relies on constructing unidentifiable conditional densities using identifiable densities and borrows techniques from standard multiple imputation.

1. Non-Future Dependent Missing Assumption

Assume there are T designed visits in a longitudinal study and let y_i (i = 1,2,...,T) represent subject's measurement at Visit i. When the missing mechanism is monotone, the pattern of missing data can be defined by the number of measurements (L) actually observed from the subject. Let $f(y_i,...,y_j \mid L=t)$ denote the conditional density of $y_i,...,y_j$, given that the last observed measurement is at Visit t. Then the overall density function for Pattern t can be written as

$$f(y_{1},...,y_{T} | L = t) = f(y_{1},...,y_{t} | L = t) f(y_{t+1} | y_{1},...,y_{t}, L = t)$$

$$\times \prod_{s=t+2}^{T} f(y_{s} | y_{1},...,y_{s-1}, L = t)$$
(1)

Note on the right hand side of (1) the first factor is clearly identifiable from the observed data, while the second and the beyond are not, due to lack of available data. The second factor $f(y_{t+1} \mid y_1,...,y_t, L=t)$ could be identifiable based on an assumed relationship between $f(y_{t+1} \mid y_1,...,y_t, L=t)$ and $f(y_{t+1} \mid y_1,...,y_t, L \ge t+1)$. The third and beyond factors $f(y_s \mid y_1,...,y_{s-1}, L=t)$ (with all $s \ge t+2$) could be identifiable with the help of non-future dependent missing assumption.

For longitudinal data with dropouts, non-future dependent missing (NFD) mechanism (Kenward et al., 2003) assumes that the unidentifiable conditional distributions of y_s ($s \ge t + 2$), given earlier measurements, in Pattern t, is equal to the corresponding distribution in patterns $L \ge s - 1$:

$$f(y_s | y_{1,...}, y_{s-1}, L = t) = f(y_s | y_{1,...}, y_{s-1}, L \ge s - 1)$$
 (2)

Page 53 of 53

The right hand side of (2) can further be partitioned into

$$f(y_s \mid y_1,..., y_{s-1}, L \ge s-1) = \sum_{j=s-1}^{T} \omega_{s-1,j} \cdot f(y_s \mid y_1,..., y_{s-1}, L = j)$$
 (3)

Where mixture probabilities $\omega_{s-1,j}$ are:

$$\omega_{s-1,j} = \frac{\alpha_j f(y_l, ..., y_{s-1} \mid L = j)}{\sum_{t=s-1}^{T} \alpha_t f(y_l, ..., y_{s-1} \mid L = t)}, \text{ and } \alpha_j \text{ represents the fraction of}$$

$$(4)$$

subjects from Pattern j.

E ach factor of the unidentifiable conditional distribution of y_s ($s \ge t + 2$) on the right side of (1) can be expressed using the following:

- $f(y_s | y_1,...,y_{s-1}, L = s-1)$, the unidentifiable conditional distribution of the first missing in pattern s-1,
- $f(y_s \mid y_1,...,y_{s-1}, L = j)$, the identifiable conditional distributions of y_s given $y_1,...,y_{s-1}$ of pattern j $(j \ge s)$, and
- α_i , the fraction of subjects from pattern j ($j \ge s 1$).

So under NFD, all the unidentifiable conditional distribution on the right side of (1) can be estimated and missing value could be therefore imputed based on the assumption for unidentifiable conditional distribution of the first missing.

We re-formulate the partition in (3), for $s \ge t + 2$, as the following:

$$f(y_s \mid y_1, ..., y_{s-1}, L = t) = \delta_{s-1} f(y_s \mid y_1, ..., y_{s-1}, L = s - 1) + (1 - \delta_{s-1}) f(y_s \mid y_1, ..., y_{s-1}, L \ge s)$$
(5)

for $s \ge t + 2$ with $\delta_{s-1} = \omega_{s-1,s-1}$.

Page 54 of 53

Therefore, under monotone missing and NFD assumption, the unidentifiable conditional densities for Visit s in Pattern t ($s \ge t + 2$) can be expressed as a mixture distribution of $f(y_s \mid y_1,...,y_{s-1}, L = s - 1)$ - the unidentifiable conditional distribution of the first missing measurement y_s in Pattern s - 1, and $f(y_s \mid y_1,...,y_{s-1}, L \ge s)$ - the identifiable conditional distribution of y_s from all the patterns with observed data at Visit s or beyond:

$$f(y_s \mid y_l, ..., y_{s-l}, L \ge s) = \sum_{j=s}^{T} \lambda_{s-l,j} f(y_s \mid y_l, ..., y_{s-l}, L = j)$$
 (6)

where the mixture probability

$$\lambda_{s-l,j} = \omega_{s-l,j} / (1 - \omega_{s-l,s-l}) = \frac{\alpha_j f(y_l, ..., y_{s-l} \mid L = j)}{T} \quad \text{for } j \ge s, \text{ where } \alpha_j \text{ is the fraction of}$$

$$\sum_{t=s}^{T} \alpha_t f(y_l, ..., y_{s-l} \mid L = t)$$

$$(7)$$

subjects from Pattern j.

The conditional densities for the first missing are selected as:

$$f(v_s | v_{l,...}, v_{s-1}, L = s - 1) = f(v_s - \Delta | v_{l,...}, v_{s-1}, L \ge s)$$
 for $s = 2, ..., T$, (8)

Note that the two distributions only differ by a shift (Δ) parameter. When $\Delta = 0$, the missing value y_s in Pattern s-l is imputed based on the distribution of all observed data up to Visit s, as a result, leading to missing at random (MAR) missingness. When $\Delta \neq 0$, (8) will introduce a scenario of MNAR. The similar idea was also presented in the recent publication "The Prevention and Treatment of Missing Data in Clinical Trials" by the National Academies Press. The selection of the plausible values for the shift parameter (Δ) is discussed in Section 3 of this appendix.

Note that per recommendation in Wang and Daniels (2011), only the observed data within pattern is assumed to be multivariate normal. The observed data distribution can be expressed in terms of the marginal distribution of baseline measurement and the conditional distributions of postbaseline measurements given earlier measurements. Assuming that these distributions are normal, the linear regression of each observation on prior observations will yield least-squares estimates of model parameters that can be utilized for independent posterior draws of model parameters for observed data. Multiple imputation approach will be used to estimate the overall mean at the final time point.

Page 55 of 53

2. Imputation Procedure

All the missing data will be imputed to create complete datasets, then statistical analysis can be performed using appropriate techniques such as ANCOVA. The imputation can accommodate MNAR missing data mechanisms, based on the theory discussed in the previous section.

The model parameters for each dropout pattern, i.e., the mean, variance and proportions of observations in each pattern, are drawn from their posterior distributions prior to the imputation of missing data for a single imputation.

The details of imputation within a pattern, say Pattern t, are as the following:

Step 1. Impute the first missing value v_{t+1} for each subject in Pattern t (t = 1, ..., T-1):

- a. Compute estimates of mixture probabilities $\lambda_{s-l,j}$ in (7) with s = t+1 given the posterior draw of proportions of observations in each pattern and the posterior draw of regression parameters for the observed data.
- b. Draw a random integer from $\{s, ...T\}$ to index a component distribution on the right hand side of (6), using mixture probabilities obtained in a). Draw y_{t+1}^* from the identified component normal distribution. Impute the missing y_{t+1} as $\widetilde{y}_{t+1} = y_{t+1}^* + \Delta$.

Step 2. Impute the rest of the missing values of $y_{t+2}, y_{t+3}, ..., y_T$ for subjects in Pattern t:

Starting with imputation for y_{t+2} , first, similar to Step 1, draw y_{t+2}^* from the normal mixture (6) based on the observed $y_1,...,y_t$ and the already imputed \tilde{y}_{t+1} for the subject.

Then the missing y_{t+2} is imputed as $\widetilde{y}_{t+2} = y_{t+2}^* + \Delta$ with probability δ_{t+1} and as $\widetilde{y}_{t+2} = y_{t+2}^*$ with probability $I - \delta_{t+1}$, where the mixture probability $\delta_{t+1} = \omega_{t+1,t+1}$ is obtained from (4) given the posterior draw of proportions of observations in each pattern and the posterior draw of regression parameters for the observed data.

Missing values of y_{t+3} through y_T can be imputed similarly as y_{t+2} .

To summarize, the imputations of y_{t+1} through y_T is done recursively within each Pattern t (for all t = 1,..., T - 1) to create a complete dataset after imputation is done for all patterns with missing values.

Page 56 of 53

The above imputation procedure is applied to all subjects in each missing data pattern to create a single imputed data set. Repeating the process of drawing parameters from the posterior distribution and imputing missing data given the posterior draw m times will yield m imputed data sets. The observed or imputed values at the final data point are averaged to obtain the overall mean estimate for each imputed data set, and the multiple imputation estimate is obtained by averaging the estimates across m imputations.

In this sensitivity analysis, m is set to equal to 20. The value of m is discussed in the context of imputation efficiency in standard multiple imputation theory (Rubin, 1987, p. 114), and m = 20 would provide at least 96% of relative efficiency as compared with using an large number of imputations (SAS/STAT User's Guide, p. 3796).

3. Determination of the Shift Parameter Values

The common shift parameter Δ is the difference between the mean of y_{t+1} among those who drop out at Visit t and those who remain beyond Visit t ($1 \le t \le T - 1$). The exact value of Δ is unknown and can't be estimated from data because of missingness. The magnitude of Δ depends on the medical aspects of the trial. Using relevant historical data, one may select Δ as a proportion of the sample standard deviation or a proportion of observed treatment efficacy.

References:

Rubin DB. Multiple Imputation for Nonresponse in Surveys. J. Wiley & Sons, New York; 1987.

SAS Institute Inc. SAS/STAT 9.2 User's Guide, Second Edition. Cary, NC: SAS Institute Inc; 2009.

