9.1.2 Analysis of Primary Parameter

The primary efficacy parameter is the change from baseline to Week 8 in PARS severity. The PARS severity score for GAD is assessed for all symptoms identified in the generalized anxiety section of the PARS symptom checklist. The PARS severity score for GAD will be derived by summing 5 of 7 severity/impairment/interference items (2, 3, 5, 6, and 7). If any of the items is missing, the severity score will be considered missing.

The primary analysis will be performed using an MMRM with treatment group, age group strata (7-11 vs. 12-17 years), sex, pooled study center, visit, and treatment group-by-visit interaction as the fixed effects and the baseline value and baseline value-by-visit interaction as the covariates. An unstructured covariance matrix will be used to model the covariance of within-subject scores. The Kenward-Roger approximation (Kenward and Roger, 1997) will be used to estimate denominator degrees of freedom. If the model convergence for the unstructured covariance matrix fails, then the Fisher scoring

Page 25 of 53

algorithm will be used to provide better initial values of the covariance parameters. In the event that the model still does not converge after using those initial values, simplified covariance structures will be used to fit the model in the following order until the model converges: (1) ante-dependence, (2) heterogeneous autoregressive, (3) Toeplitz, and (4) compound symmetry. If a structured covariance is used, then a robust sandwich estimator will be used for estimating the variance of the treatment effect estimate.

This analysis will only use the observed cases of post-baseline scores without imputation of missing values. The significance test for the difference in means at Week 8 will be based on least squares (LS) means using a 2-sided α of 0.05. Differences between treatments at the other post-baseline visits will also be estimated based on LS means.

The primary analysis will treat measurements after study withdrawal as missing in the MMRM modeling, leading to an estimate of the treatment effect while on treatment. Two sensitivity analyses, last observation carried forward (LOCF) and pattern-mixture model, will be performed on the primary efficacy parameter to assess the impact of the missing at random assumption of MMRM.

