For the LOCF approach, only the postbaseline PARS severity score for GAD will be imputed; individual item scores will not be carried forward to derive the PARS severity score. Baseline total score will be carried forward only for the missing scores immediately after baseline. If all the postbaseline values are missing, the baseline value will not be carried forward. The LOCF approach is based on an analysis-of-covariance (ANCOVA) model including treatment group and pooled study center as factors and baseline PARS severity score as a covariate

Another sensitivity analysis using a pattern-mixture model approach based on non-future dependent missing value restrictions (Kenward et al., 2003) will be performed to assess the robustness of the primary MMRM results to the possible violation of the missing-at-random assumption. The details of this sensitivity analysis are as follows:

The pattern for the pattern-mixture model will be defined by the subject's last visit with an observed value. The observed PARS severity score at a visit is assumed to have a linear relationship with the subject's prior measurements. The missing values will be imputed under the assumption that the distribution of the missing observations differs from that of the observed only by a shift parameter value Δ . The dataset with missing values imputed will be analyzed using an analysis of covariance (ANCOVA) model with treatment group and pooled study center as factors and baseline PARS severity score as a covariate for between–treatment group comparisons at Week 8. The imputation of missing values and the analysis will be performed multiple times and the inference of this sensitivity analysis will be based on the combined estimates using the standard multiple imputation technique. The shift parameter values Δ for the multiple imputation will start at 0 and increase by 1 to 6 or until a tipping point is reached (ie, the p-value switches from ≤ 0.05 to ≥ 0.05), whichever is higher.

Page 26 of 53

More details of the proposed pattern-mixture model approach (e.g., the models for the pattern-specific identifiable densities and the unidentified conditional distributions, the shift parameter Δ , and the multiple imputation algorithm) are provided in Appendix I to this SAP.

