13.0 BLINDED INTERIM ANALYSIS

A blinded interim analysis will be conducted when approximately 75% of randomized subjects have either completed the study or discontinued from the study. The blinded interim analysis is to obtain an estimate of the pooled standard deviation of the change from baseline in the PARS score to Week 8 of the double-blind acute treatment period. The sample size will be re-estimated using simulation in the same manner as the original sample size as described in Section 14 using the estimated pooled standard deviation and dropout rate from the blinded interim analysis. If the estimated pooled standard deviation is larger than the assumed pooled standard deviation due to assumption deviation as well as COVID-19 remote visits or dropout rate is increased, the sample size in placebo and escitalopram treatment groups may be increased to ensure an adequate power. However, due to the difficulties in recruiting pediatric subjects with GAD, the number of subjects in each treatment arm will be capped at 160.

As the sample size re-estimation requires only the pooled standard deviation and dropout rate to be updated, all data and personnel will remain blinded for the interim analysis. Randomization code will not be released for the sample size re-estimation. There are no potential unblinding issues in the sample size re-estimation. As this is a blinded re-estimation, there is no impact on the overall Type I error rate of the study.

SAP SCT-MD-60 Allergan

Page 40 of 53

14.0 DETERMINATION OF SAMPLE SIZE

The sample size estimate was constructed using a simulation approach as described in Lu K. (2012).

The primary efficacy parameter is the change from baseline to Week 8 of the double-blind acute treatment period in PARS total score. To detect an effect size (treatment group difference of 2.30 units relative to pooled standard deviation of 5.79) of 0.39, a sample size of 128 subjects in the escitalopram treatment group and 128 subjects in the placebo group will provide 85% power based on an MMRM model using simulation method. The simulation assumed a correlation of 0.7 between the repeated measures, and a common dropout rate of 14%, based on historical data of escitalopram in pediatric subjects.

SAP SCT-MD-60 Allergan

Page 41 of 53

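### Twenty imputations are too few to make the tipping point reproducible across random seeds, and the relative-efficiency argument for m = 20 does not address that

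*SAP*

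**What the plan says.** SAP Section 9.1.2 names two checks of the missing-at-random assumption behind the primary MMRM: LOCF and a pattern-mixture model with multiple imputation. In the second, the shift values "will start at 0 and increase by 1 to 6 or until a tipping point is reached", and the search runs to the higher of those two limits. Tipping is defined as the point where "the p-value switches from ≤ 0.05 to ≥ 0.05".

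Appendix I, part 2, fixes the number of imputations ("In this sensitivity analysis, m is set to equal to 20") and gives one reason: "m = 20 would provide at least 96% of relative efficiency as compared with using an large number of imputations".

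The SAP gives no seed and no Monte Carlo error for the estimate or for p. It does not say whether the same random draws are used at each shift. Section 9.1.2 names no arm for the shift. Appendix I, part 3, calls it common ("The common shift parameter Δ is the difference between the mean of" ...), so both readings are examined below.

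**The concern.** Relative efficiency compares the variance of the pooled estimate at m imputations with its variance at very many. It can be close to 1 while p still varies visibly from one seed to another. For most uses of multiple imputation that variation is harmless. Here the reported result is the grid value at which p passes a fixed threshold, so small noise in p can move the answer by a whole step or more.

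At stake is the location of the tipping point, which the report would use to say how far the data must depart from missing at random before significance is lost. Without a prespecified seed, a reader cannot tell how much of that location comes from the data and how much from the random numbers.

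**Working it through.** **Inputs.** SAP Section 14.0: "treatment group difference of 2.30 units relative to pooled standard deviation of 5.79", 128 per arm, correlation 0.7, dropout 14%. SAP Section 9.1.2: tests "using a 2-sided α of 0.05", unit-step grid. Schedule of assessments: post-baseline PARS at Weeks 2 and 8 only. Protocol Section 8.3.1: about 115 per arm with a post-baseline assessment.

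**How many are imputed.** 14% of 128 is about 18 dropouts per arm. If all have a Week 2 score, 18 of 128 are imputed. If 128 − 115 = 13 have no post-baseline score, they are outside the mITT population and 18 − 13 = 5 of 115 are imputed. Both cases are carried.

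**The plan's own figure.** Relative efficiency is 1/(1 + λ/m), where λ is the fraction of missing information. At m = 20:

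| λ | Efficiency |
|---|---|
| 0.02 | 99.9% |
| 0.09 | 99.6% |
| 0.83 | 96.0% |
| 1.00 | 95.2% |

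Simulated λ is about 8–9% with 18 of 128 imputed and about 2% with 5 of 115. The two-visit variance factor (1 − ρ²)/(1 − d) + ρ² agrees:
- d = 18/128: 0.51/0.859 + 0.49 = 1.083, so λ = 1 − 1/1.083 = 0.077.
- d = 5/115: 0.51/0.957 + 0.49 = 1.023, so λ = 0.023.

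The efficiency claim is therefore met comfortably in this trial.

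**Noise in z against the change per step.** The seed-to-seed SD of z is about √(λ/m). A unit shift in the escitalopram arm moves its mean by the imputed fraction d, so z changes by about d/SE, with SE = 5.79·√(2/n).

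| | 18 of 128 | 5 of 115 |
|---|---|---|
| SE | 0.724 | 0.764 |
| z change per step | 0.141/0.724 = 0.194 | 0.0435/0.764 = 0.057 |
| SD of z, m = 20 | √(0.09/20) = 0.067 | √(0.02/20) = 0.032 |
| r = SD ÷ step | 0.35 | 0.56 |

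Fewer imputed subjects mean less noise, but the z change per step shrinks faster.

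**Disagreement between two seeds, closed form.** With draws reused across shifts, the noise moves the whole curve. The crossing points from two seeds then differ by D ~ N(0, 2r²) grid steps. If the crossing falls anywhere within a step with equal chance, P(different grid value) = E[min(|D|, 1)]. For an escitalopram-only shift this gives 0.38 (18 of 128) and 0.55 (5 of 115). At m = 1000, r falls by √(20/1000) = 0.141, giving 0.055 and 0.089.

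**Simulation on the same inputs** (true effect 2.30, two-arm mean comparison, draws reused, data sets that tip after shift 0 and by shift 30). Probability that two seeds differ at m = 20:

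| | Escitalopram-only shift | Common shift |
|---|---|---|
| 18 of 128 | about 38% | about 67% |
| 5 of 115 | about 55% | about 72% |

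At m = 1000 the figures are about 6–14%.

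**Second simulation**, using ANCOVA with treatment and baseline, 18 of 128, and 150 data sets significant at shift 0:

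| | m = 20 | m = 100 | m = 500 |
|---|---|---|---|
| Escitalopram-only shift | 39% | 18% | 9% |
| Common shift | 60% | 33% | 17% |

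The common-shift row covers the data sets that tip by shift 30. Disagreement is higher there because equal dropout largely cancels the shift: z changes by about 0.08 per step, with a seed SD of 0.051. At m = 20 the central 95% range of the tipping point over seeds averages 1.4 steps (escitalopram only) and 2.8 steps (common). Setting the correlation to 0.5, dropout to 25% or the true effect to 1.8, one at a time, gives 37–46% for the escitalopram-only shift.

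**The case against.** **The 96% figure.** A reader might infer that "at least 96% of relative efficiency" is mistaken, since the formula gives 95.2% at λ = 1. The documents do not support that criticism for this trial. Falling below 96% needs λ above 0.83, while 14% dropout implies 2–9% and an efficiency of at least 99.5%. The figure is sound; it answers a different question.

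**The p-value range.** For a data set whose large-m p is about 0.049, p at m = 20 runs from 0.034 to 0.068 over seeds with 18 of 128 imputed, and from 0.042 to 0.058 with 5 of 115. These ranges are conditional on p lying at the threshold and say nothing about how often that happens. The objection stands, so the size of the problem is taken from the tipping-point comparisons instead.

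**False or missed tipping points.** A reader might also infer that the plan could report a tipping point where none exists, or miss one. The rule in Section 9.1.2 continues past 6 until tipping occurs, so the search does not stop short. What moves is the location. Significance at every shift from 0 to 6 differs between two seeds in only about 1–4% of unselected trials. The looser event, at least one of 100 seeds differing, occurs in 8–15% of data sets, but a report uses one seed.

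**Low stakes.** The primary MMRM imputes nothing, and LOCF has no Monte Carlo error. That is correct and keeps this a minor point. Reuse of draws may already be intended, but the SAP does not say so.

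**Conclusion.** The point holds as a minor one. At m = 20 the reported tipping point depends on the seed to a degree that the SAP's justification does not cover: two seeds disagree in about 38–72% of comparisons, depending on the arm shifted and the number imputed. The typical movement is about one grid step for an escitalopram-only shift and more for a common shift. The documents do not support the stronger reading that the overall robustness conclusion, or the primary result, turns on the seed.

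The figures are conditional on data sets that are significant at shift 0 and tip by shift 30. They also assume that missingness is at random after Week 2, that imputation is done within arm, that change is unrelated to baseline, that there is no centre term, and that draws are reused across shifts. The last favours the plan, because fresh draws at each shift would be expected to add noise.

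**What to change.** In SAP Appendix I, part 2:
- Replace m = 20 with m = 1000, or at least 500.
- State the random seed. This removes any choice of seed after the fact but does not reduce the noise, so it complements the larger m.
- State that the same parameter and residual draws are used at every shift, so that p changes only through the shift.
- Replace the efficiency sentence with a commitment to report the Monte Carlo error of the pooled estimate, and of p at the shifts around the tipping point.

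The cost is a short SAP edit and computing time. No data collection, alpha or primary analysis changes. The edit should be made before unblinding, while a prespecified seed still has value.
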